For Intervention Phase: 
 Exposure to CAB+RPV Oral Lead-in = IP (oral lead-in) stop date - IP (oral lead-in) start date +1 Exposure to CAB LA + RPV LA = Number of IP injection visits received during the Intervention Phase (up to but not including injections administered at Month 13) Exposure to SOC oral bridging: Duration of the SOC ART medication taken as oral bridging during the Intervention Phase. If the SOC oral bridging is taken in different periods during the Intervention Phase, the duration will be calculated by the sum of non-overlapped periods. Exposure to CAB+RPV Oral Bridging (COVID-19 Related): Duration of the CAB+RPV taken as oral bridging for reasons related to COVID-19 during the Intervention Phase. If COVID-19 related CAB+RPV oral bridging is taken in different periods during the Intervention Phase, the duration will be calculated by the sum of the non-overlapped periods. Exposure to CAB+RPV Oral Bridging (Non COVID-19 Related): Duration of the CAB+RPV taken as oral bridging for reasons not related to COVID-19 during the Intervention Phase. If non COVID-19 related CAB+RPV oral bridging is taken in different periods during the Intervention Phase, the duration will be calculated by the sum of the non-overlapped periods. Overall Exposure to Study Treatment: min [Date of Latest Intervention Phase Visit up to and including Month 13, max (Date of Last Injection + 35, Date of Last Dose of Oral CAB+RPV, Date of Last Dose of SOC Oral Bridging)] – min (Start Date for Oral lead-in CAB+RPV, Date of First CAB/RPV Injection) + 1 
 Note: Conditions in the above formula pertaining to Last Injection/Last Dose of Oral CAB+RPV/Last Dose of SOC Oral Bridging are only applicable to those who permanently discontinued study treatment. 	

Other Safety Endpoints	

 • Overall Exposure to CAB + RPV = Overall Exposure to Study Treatment – Exposure to SOC Oral Bridging 	
For Intervention + Extension Phase:	

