
 • Exposure to CAB LA + RPV LA = Number of IP injection visits received during Intervention Phase and Extension Phase • Exposure to SOC or CAB+RPV Oral Bridging during the Intervention and Extension Phase will be calculated similarly to that during the Intervention Phase except that the exposure includes both Intervention and Extension Phase. • Overall Exposure to Study Treatment: min [Date of Latest Intervention/Extension Phase Visit, max (Date of Last Injection + 35, Date of Last Dose of Oral CAB+RPV, Date of Last Dose of SOC Oral Bridging)] – min (Start Date for Oral lead-in CAB+RPV, Date of First Study Injection) + 1 
 ○ Note: Conditions in the above formula pertaining to Last Injection/Last Dose of Oral CAB+RPV/Last Dose of SOC Oral Bridging are only applicable to those who permanently discontinued study treatment. • Overall Exposure to IP = Overall Exposure to Study Treatment – Exposure to SOC Oral Bridging • Duration of dosing in participant years will be calculated as the sum of participant duration of dosing in days (across all participants)/365.25 	

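### Exposure to CAB + RPV is understated when SOC bridging runs past the latest phase visit, because those days are subtracted from a total that never counted them

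*SAP*

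**What the plan says.** All of this is in SAP Section 13.6.4, under Extent of Exposure.

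- **Total, Intervention Phase.** The end date is "min [Date of Latest Intervention Phase Visit up to and including Month 13, max (Date of Last Injection + 35" and, inside the same maximum, the last oral CAB+RPV dose and the last SOC bridging dose. A note says that the last-dose conditions "are only applicable to those who permanently discontinued study treatment". For everyone else the end date is simply the latest visit.
- **SOC bridging.** This is the "Duration of the SOC ART medication taken as oral bridging during the Intervention Phase". With several periods, "the duration will be calculated by the sum of non-overlapped periods". No upper date is given.
- **CAB + RPV, Intervention Phase.** This is "Overall Exposure to Study Treatment – Exposure to SOC Oral Bridging", the total minus the SOC bridging duration.
- **Intervention + Extension.** The end date has the same form, "min [Date of Latest Intervention/Extension Phase Visit, max (Date of Last Injection + 35", and the subtraction is repeated: "Overall Exposure to IP = Overall Exposure to Study Treatment – Exposure to SOC Oral Bridging".

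Table 9 in Section 13.4.1 fixes which medication days belong to a phase. For a participant who does not continue into the Extension, the Intervention Phase runs until long-term follow-up ART starts. If that start date is missing, the phase has no upper limit.

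**The concern.** The two terms of the subtraction cover different intervals. The outer minimum ends the total at the latest visit at the latest. The SOC term runs to the end of the phase as Table 9 defines it, which can be later. SOC days between those two dates appear only in the term being subtracted.

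The SAP itself foresees the situation. Section 13.6.2 (adherence to the injection schedule) provides for participants whose last study treatment is oral bridging and for bridging still ongoing at a data cut. Section 13.9 ties SOC bridging to study product being unavailable during the pandemic, and also notes that the pandemic limits clinic attendance.

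At stake is the per-participant exposure to the investigational product behind the exposure summaries (Tables 3.1 and 3.2). A programmer who follows the text produces the understated value; one who truncates silently departs from the plan.

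**Working it through.** The SAP gives no exposure figure to reproduce, so the check applies its formulas to illustrative participants. All study days below are assumptions; treatment starts on Day 1.

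**Formulas (Section 13.6.4)**

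- Permanent discontinuer: end = min(latest visit, max(last injection + 35, last oral CAB+RPV, last SOC dose)).
- Otherwise: end = latest visit.
- Total = end - 1 + 1 = end.
- CAB + RPV as written = total - all SOC bridging days in the phase.
- CAB + RPV aligned = total - SOC bridging days up to the end date.

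**Discontinuer, last visit and injection Day 240, SOC Days 271-360, no later visit**

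- End = min(240, max(275, 360)) = 240, so total = 240.
- SOC = 360 - 271 + 1 = 90, all after Day 240.
- As written: 240 - 90 = 150. Aligned: 240 - 0 = 240. Understated by 90 days, or 90/240 = 37.5% for this one participant.

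**Other cases**

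| Case | Total | SOC days | As written | Aligned | Understated by |
|---|---|---|---|---|---|
| A. Discontinuer, last injection Day 120, SOC Days 151-180, last visit Day 200 | min(200, max(155, 180)) = 180 | 30 | 150 | 150 | 0 |
| B. Discontinuer, last injection Day 120, last visit Day 150, SOC Days 151-210 | min(150, max(155, 210)) = 150 | 60 | 90 | 150 | 60 |
| C. Discontinuer, only injection and last visit Day 30, SOC Days 60-120 | min(30, max(65, 120)) = 30 | 61 | -31 | 30 | 61 |
| D. Still on treatment, last visit Day 300, SOC Days 290-330 | 300 | 41 | 259 | 300 - 11 = 289 | 30 |

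In case D, Days 290-300 (11 days) are inside the total and are rightly removed; Days 301-330 (30 days) are not. Moving every date in D later by the same amount, so that the last visit falls in the Extension, leaves the 30 unchanged.

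**When the result turns negative.** Let SOC start 31 days after the last visit and last 30, 60, 90, 120 or 180 days:

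| Last visit | 30 | 60 | 90 | 120 | 180 |
|---|---|---|---|---|---|
| Day 30 | 0 | -30 | -60 | -90 | -150 |
| Day 61 | 31 | 1 | -29 | -59 | -119 |
| Day 91 | 61 | 31 | 1 | -29 | -89 |
| Day 183 | 153 | 123 | 93 | 63 | 3 |

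In every case the understatement equals the number of SOC days after the end date of the total. Nothing in the SAP limits the SOC term to that date or sets a floor at zero.

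**The case against.** The best defence is that few participants can meet the conditions. The schedule in Section 13.2.1.1 has a withdrawal visit, and some participants get a further contact about four weeks after the last dose. If any visit in the phase falls on or after the last bridging day, the formula is right (case A). ART from the start of long-term follow-up ART onward is outside the phase and is not subtracted. SOC bridging is confined to product unavailability in the pandemic, and oral CAB+RPV bridging is not subtracted at all. No hypothesis is tested (Section 2.4), and Listings 12 and 45 would show the underlying data. All of this stands: it limits how often the error occurs. It does not supply the missing cut-off.

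Four stronger conclusions might be drawn, and the documents do not support them:

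- **That participant-years are wrong.** Section 13.6.4 builds them from a duration of dosing without saying which duration. If it is the overall total, nothing is subtracted and there is no error.
- **That Table 3.1 is wrong for anyone bridging at the Month 12 cut-off.** That analysis follows completion of Month 12 by all participants (Section 3.2). For those who attend Month 13 and continue, medication in the Intervention Phase and the total both end at that visit, so the terms match. Bridging past the last visit at a data cut matters for the Intervention + Extension summary (Table 3.2). Even there, Section 13.7.2.1 treats ART with no stop date as ongoing without giving its duration an end, so the days subtracted would depend on the programmer.
- **That negative exposure is to be expected.** It requires more SOC days after the last visit than non-SOC days before it, which in practice means an early last visit.
- **That a loss such as 37.5% describes a table.** It describes one invented participant.

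**Conclusion.** The derivation is wrong as written for a narrow group: participants with SOC bridging days after their latest phase visit. The clearest examples are a discontinuer whose last treatment is SOC bridging with no later visit, and bridging that extends past the last visit at a data cut in the Intervention + Extension summary. For them, exposure to CAB + RPV (or IP) is too low by exactly one day per such day. Everyone else is unaffected.

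This rests on reading the SOC duration through the phase limits of Table 9, the only phase rule the SAP gives for medications. The number affected is not stated and is probably small, so the effect on the tables cannot be sized. It is a minor point, worth correcting because the wrong value follows directly from the stated rule.

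**What to change.** In Section 13.6.4, for both the Intervention Phase and the Intervention + Extension formulas, subtract only those SOC bridging days that fall between the start date and the end date used for the overall total. For bridging with no stop date, the same end date then closes the interval. The separately reported SOC bridging duration can stay as defined.

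The cost is one phrase in each formula and one line of code. No new data are needed, and no clinical rule changes.

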13.6.5. Virology

Genotype	
Amino Acid Changes	
• A mutation is considered present whenever the encoded amino acid residue differs from the amino acid that would have been encoded by the wild-type (e.g., HXB2, NL43) comparator gene; e.g., Q148K.	
• If the encoded amino acid is seen as a mixture of wild-type and mutant amino acid, e.g., Q148Q/K, the mutated amino acid is considered present at the codon of interest.	
• If the encoded amino acid is seen as a mixture of two or more amino acids, which may or may not include wild type, e.g., Q184K/H or Q184K/H/Q, etc., for the purposes of calculating the number of mutated amino acids, only one mutation is considered to be present at the codon of interest.	
Representation of Amino Acid Changes	
Mutations	Amino Acid Change
T69S	Single mutation from amino acid 'T' (vendor reference) to 'S' (sample) at codon '69'
Q148H/K/R	Mixture of amino acid mutations 'H', 'K' and 'R' (sample) from amino acid 'Q' (vendor reference) at codon '148'
_69_1T	First insertion of amino acid 'T' (sample) at codon '69'
_69_2S	Second insertion of amino acid 'S' (sample) at codon '69'
_69_3S/A	Third insertion of a mixture of amino acids 'S' and 'A' (sample) at codon '69'

Genotype	
L74L-	Mixture of amino acid 'L' (sample) and a deletion at codon '74'
V75-	Single deletion of amino acid (sample) at codon '75'
Resistance Associated mutations	
Known INI mutations associated with the development of resistance to Integrase Strand Transfer Inhibitors:	
Amino Acids in HIV Integrase for Analysis	H51Y, T66A/I/K , L68V/I, L74I/M, E92Q/V/G , Q95K, T97A, G118R , F121Y , E138A/D/K/T, G140A/C/R/S , Y143C/H/R/K/S/G/A , P145S, Q146P, S147G , Q148H/K/R/N , V151/I/L/A, S153F/Y, N155H/S/T , E157Q, G163R/K, G193E, S230R, R263K

 • Draft listing; may be modified in case of additional substantive data availability. • Based on the IAS-USA list of mutations associated with resistance to Bictegravir, Cabotegravir, Dolutegravir, Elvitegravir, or Raltegravir (IAS-USA 2019 resistance mutations update volume 27 issue 3, 2019): T66A/I/K, L74M, E92Q/G, T97A, G118R, F121Y, E138A/K/T, G140A/C/R/S, Y143C/H/R, S147G, Q148H/K/R, S153F/Y, N155H, R263K) and observed mutations during in vitro passage of DTG or seen in a previous DTG study in INI-experienced subjects (study ING112574): H51Y, L74I, L68V/I, E92V, Q95K, E138D, Y143K/S/G/A, P145S, Q146P, V151/I/L/A, N155S/T, E157Q, G163R/K, G193E, S230R. • Major USA-IAS mutations associated with resistance to INSTI are bolded. • Major resistance mutations to other classes (i.e., NRTI, NNRTI, PI) as defined by the International Antiviral Society-USA (IAS-USA). The most up to date IAS-USA guidelines available at the time of DBF will be used in the analysis [Wensing, 2019]. 	
Class	Mutations
NRTIs	M41L, A62V, K65R/E/N, D67N, 69 insert, K70E/R, L74V, V75I, F77L, Y115F, F116Y, Q151M, M184V/I, L210W, T215Y/F, K219Q/E
NNRTIs	L100I, K101E/P, K103N/S, V106A/M, V108I, E138/A/G/K/Q/R, V179L, Y181C/I/V, Y188C/L/H, G190S/A, H221Y, P225H, F227C, M230I/L
PIs	D30N, V32I, M46I/L, I47A/V, G48V, I50V/L, I54V/M/L, Q58E, T74P, L76V, V82A/T/F/L/S, N83D, I84V, N88S, L90M

 • Draft listing; may be modified in case of additional substantive data availability. 	

13.6.6. Other Assessments

Study Visit Length	

 • Lead Time = Actual Start Time of Appointment – Arrival Time • Process Time = Actual End Time of Appointment – Actual Start Time of Appointment • Total Time = Actual End Time of Appointment – Arrival Time 	

13.7. Appendix 7: Reporting Standards for Missing Data

13.7.1. Premature Withdrawals

Element	Reporting Detail
General	
 Withdrawn participants were not replaced in the study. All available data from participants who were withdrawn from the study will be listed and all available planned data will be included in summary tables and figures, unless otherwise specified. Withdrawal visits will be slotted according to Appendix 3: Assessment Windows (excluding PK data)

13.7.2. Handling of Missing Data

Element	Reporting Detail
General	
 Missing data occurs when any requested data is not provided, leading to blank fields on the collection instrument: 
 These data will be indicated by the use of a “blank” in participant listing displays. Unless all data for a specific visit are missing in which case the data is excluded from the table. Answers such as “Not applicable” and “Not evaluable” are not considered to be missing data and should be displayed as such.
Outliers	
 Any participants excluded from the summaries and/or statistical analyses will be documented along with the reason for exclusion in the clinical study report.

13.7.2.1. Handling of Missing and Partial Dates

Element	Reporting Detail		
General	
 Partial dates will be displayed as captured in participant listing displays. Where necessary, display macros may impute dates as temporary variables for sorting data in listings only. In addition, partial dates may be imputed for ‘slotting’ data to study phases or for specific analysis purposes as outlined below. 		
Adverse Events	
 Imputations in the adverse events dataset are used for slotting events to the appropriate study time periods and for sorting in data listings. Partial dates for AEs recorded in the CRF will be imputed using the following conventions: 
 
 Missing start day	 
 If study treatment start date is missing (i.e. participant did not start study treatment), then set start date = 1st of month. Else if study treatment start date is not missing: 
 If month and year of start date = month and year of study treatment start date, then 	
 
 	Missing start day	
 If study treatment start date is missing (i.e. participant did not start study treatment), then set start date = 1st of month. Else if study treatment start date is not missing: 
 If month and year of start date = month and year of study treatment start date, then
Missing start day	
 If study treatment start date is missing (i.e. participant did not start study treatment), then set start date = 1st of month. Else if study treatment start date is not missing: 
 If month and year of start date = month and year of study treatment start date, then 		

Element	Reporting Detail			
		
 ▪ If stop date contains a full date and stop date is earlier than study treatment start date, then set start date = 1st of month. ▪ Else set start date = study treatment start date. ○ Else 
 ▪ For Non-ISR AEs: set start date = 1st of month ▪ For ISR AEs: if oral bridging taken during the month and year, set start date = min(last day of the month, day of AE stop date if available, day of study treatment discontinuation if occurring during the month and year); else set start date = 1st of month. 		
	Missing start day and month	
 • If study treatment start date is missing (i.e. participant did not start study treatment), then set start date = January 1. • Else if study treatment start date is not missing: 
 ○ If year of start date = year of study treatment start date, then 
 ▪ If stop date contains a full date and stop date is earlier than study treatment start date, then set start date = January 1. ▪ Else set start date = study treatment start date. ○ Else set start date = January 1. 		
	Missing stop day	Last day of the month will be used.		
	Missing stop day and month	No Imputation		
	Completely missing start/end date	No imputation		
	
 • Completely missing start or end dates will remain missing, with no imputation applied. 			
Non-ART Medications	
 • Partial dates for any concomitant medications recorded in the CRF will be imputed using the following convention: 
 
 Missing start day	 
 • If study treatment start date is missing (i.e. participant did not start study treatment), then set start date = 1st of month. • Else if study treatment start date is not missing: 
 ○ If month and year of start date = month and year of study treatment start date, then 	
 
		Missing start day	
 • If study treatment start date is missing (i.e. participant did not start study treatment), then set start date = 1st of month. • Else if study treatment start date is not missing: 
 ○ If month and year of start date = month and year of study treatment start date, then
Missing start day	
 • If study treatment start date is missing (i.e. participant did not start study treatment), then set start date = 1st of month. • Else if study treatment start date is not missing: 
 ○ If month and year of start date = month and year of study treatment start date, then 			

Element	Reporting Detail
	
 ▪ If stop date contains a full date and stop date is earlier than study treatment start date, then set start date= 1st of month. ▪ Else set start date = study treatment start date. 
 ○ Else set start date = 1st of month. 
Missing start day and month
 
 • If study treatment start date is missing (i.e. participant did not start study treatment), then set start date = January 1. • Else if study treatment start date is not missing: 
 ○ If year of start date = year of study treatment start date, then 
 ▪ If stop date contains a full date and stop date is earlier than study treatment start date, then set start date = January 1. ▪ Else set start date = study treatment start date. • Else set start date = January 1. 
Missing end day
 
A '28/29/30/31' will be used for the day (dependent on the month and year)
 
Missing end day and month
 
A '31' will be used for the day and 'Dec' will be used for the month.
 
Completely missing start/end date
 
No imputation
 
 • The recorded partial date will be displayed in listings. 
ART Medications
 
 • Partial dates recorded in the eCRF will be imputed using the following convention: 
 ○ If the partial date is a start date, a '01' will be used for the day and 'Jan' will be used for the month. ○ If the partial date is a stop date, a '28/29/30/31' will be used for the day (dependent on the month and year) and 'Dec' will be used for the month. • If medications recorded in the PRIOR ART form of the eCRF, then the earlier date of the imputed and the day prior to the Intervention phase treatment start date will be used, i.e. min (imputed stop date, Intervention phase treatment start date - 1). • For medications with completely missing start date, they will be considered started prior to the Intervention phase treatment start date. • For medications with completely missing stop date, they will be considered ongoing unless recorded in the PRIOR ART form of the eCRF. • For ART booster medications, the start and stop dates are not recorded in the database (i.e. missing), the dates will be imputed to be the same as the dates of their parent medications. • The recorded partial or missing date will be displayed in listings.

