13.4.2. Treatment State

Within each study phase (based on assignment of study phase described in Section 13.4.1), only those events/assessments which occur within the ranges shown in Table 10 will be considered ‘on-treatment’ for the given phase. No treatment states will be assigned to medications.

For adverse events, partial AE start date will use imputation as described in 13.7.2.1.

Table 10 Treatment State within Study Phases

Study Phase	State	Definition
Screen	Pre-Treatment	All assessments/events within phase
Intervention/Extension	On-treatment	Date \leq max (Date of Last CAB LA +RPV LA IM Dose + 35, Date of Last Dose of Oral Study Treatment (CAB+RPV or SOC Bridging) +1)
	Post-Treatment	Date $>$ max (Date of Last CAB LA +RPV LA IM Dose + 35, Date of Last Dose of Oral Study Treatment (CAB+RPV or SOC Bridging) +1)
Long Term Follow-Up	Post-Treatment	All assessments/events within phase

NOTES:

- Date = Assessment/Start Date
- a. Treatment State is determined after data has been assigned to the study phases as defined in Section 13.4.1.
- b. Last injection and/or last dose of oral study treatment (CAB+RPV or SOC bridging) are only applied to participants who permanently discontinued the study treatment. The assessments for participants who did not permanently discontinue the study treatment will be considered 'On-treatment'. For participants continuing into extension phase, all data assigned to intervention phase per Section 13.4.1 will be considered 'On-treatment'

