13.4.3. Oral Lead-in Period

Certain displays will be produced for data collected or events occurring during the oral-lead-in period as defined in Table 11 and Table 12.

Table 11 Oral Lead-in Period for AEs

Study Period	Date Range
Oral Lead-in	
For participants receiving at least one Injection: Intervention Treatment Start Date \leq Date [a] $<$ Date of First IM Injection
 
For participants withdrawing prior to first Injection: Date \geq Intervention Treatment Start Date
 
Note that the oral lead-in period is only applicable to the participants who received at least one dose of study treatment during the oral lead-in period in the study. Oral lead-in period is within the intervention phase.

[a] AEs with completely missing start date which have been assigned to the Intervention Phase based on Table 6 will not be assigned to the Oral Lead-in Period.

NOTES:

- Date = AE Start date

Table 12 Oral Lead-in Period for Laboratory Data

Period	Date Range
Oral Lead-in	
For participants receiving at least one Injection: Intervention Treatment Start Date $<$ Date \leq Date of First IM Injection
 
For participants withdrawing prior to first Injection: Date $>$ Intervention Treatment Start Date
 
Note that the oral lead-in period is only applicable to the participants who received at least one dose of study treatment during the oral lead-in period in the study. Oral lead-in period is within the intervention phase.

NOTES:

- Date = Date of assessment

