13.13.7. Safety Tables

Note: The summary table for individual AESI may be added or removed per final AESI list for the analysis.

Safety: Tables					
No.	Population	GSK Standard/ Example Shell	Title	Programming Notes	Deliverable
Exposure					
3.1.	Safety	207966/primary_15/T3.1	Summary of Exposure to Study Treatment (Intervention Phase)		M12
3.2.	Safety	207966/primary_15/T3.1	Summary of Exposure to Study Treatment		M12, EOS
3.3.	Safety	SAF_T1 See Section 13.14	Summary of Adherence to CAB LA + RPV LA Dosing Schedule by Visit, Site Type and COVID-19 Impact /Non-Impact (Intervention Phase)	COVID Impact refers to missed or out of window injections for COVID-19 related reasons (as captured as COVID-19 related protocol deviations)	HL, M12
3.4.	Safety	SAF_T2 See Section 13.14	Summary of Adherence to CAB LA + RPV LA Dosing Schedule by Visit, Site ID and COVID-19 Impact /Non-Impact (Intervention Phase)	COVID Impact refers to missed or out of window injections for COVID-19 related reasons (as captured as COVID-19 related protocol deviations)	HL, M12

Safety: Tables					
No.	Population	GSK Standard/Example Shell	Title	Programming Notes	Deliverable
3.5.	Safety	SAF_T1 See Section 13.14	Summary of Adherence to CAB LA + RPV LA Dosing Schedule by Visit, Site Type and COVID-19 Impact /Non-Impact	COVID Impact refers to missed or out of window injections for COVID-19 related reasons (as captured as COVID-19 related protocol deviations)	EOS
3.6.	Safety	SAF_T2 See Section 13.14	Summary of Adherence to CAB LA + RPV LA Dosing Schedule by Visit, Site ID and COVID-19 Impact /Non-Impact	COVID Impact refers to missed or out of window injections for COVID-19 related reasons (as captured as COVID-19 related protocol deviations)	EOS
Adverse Events (AEs)					
3.7.	Safety	AE3	Summary of Adverse Events by Overall Frequency	ICH E3	M12, EOS
3.8.	Safety	AE5B	Summary of Adverse Events by System Organ Class and Maximum Grade	ICH E3	HL, M12, EOS
3.9.	Safety	AE5B	Summary of Adverse Events by System Organ Class and Maximum Grade — Excluding Study Drug Injection Site Reactions		M12, EOS
3.10.	Safety	AE5B	Summary of Adverse Events by System Organ Class and Maximum Grade (Oral Lead-in Period)		M12
3.11.	Safety	AE3	Summary of Common (>=5%) Adverse Events by Overall Frequency	ICH E3	M12, EOS

Safety: Tables					
No.	Population	GSK Standard/ Example Shell	Title	Programming Notes	Deliverable
3.12.	Safety	AE3	Summary of Common (>=1%) Grade 2-5 Adverse Events by Overall Frequency	ICH E3	M12, EOS

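### Adverse events dated only to the month of first injection, or only to the year, can be slotted to the oral lead-in whatever their true relation to the injection, so Table 3.10 can include post-injection events

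*SAP*

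**What the plan says.** The AE rules in SAP section 13.7.2.1 do more than sort listings: "Imputations in the adverse events dataset are used for slotting events to the appropriate study time periods". Section 13.4.2 repeats the link: "For adverse events, partial AE start date will use imputation as described in 13.7.2.1".

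- **Day missing.** If the month is the treatment-start month, the rule is "Else set start date = study treatment start date", except when a full stop date precedes treatment start. In any other month, "For Non-ISR AEs: set start date = 1st of month". Injection-site reactions (ISRs) follow the same rule unless oral bridging was taken that month, in which case a late date is used.
- **Day and month missing.** The rule opens "If year of start date = year of study treatment start date, then" and again leads to the treatment start date, with the same stop-date exception. Any other year becomes January 1. There is no separate provision for ISRs here.
- **Oral lead-in window (Table 11).** For participants with at least one injection, an AE is in the lead-in if its date is on or after treatment start and before the "Date of First IM Injection".
- **No date at all.** Footnote [a] to Table 11 says that "AEs with completely missing start date which have been assigned to the Intervention Phase based on Table 6 will not be assigned" to the lead-in.

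The display concerned is Table 3.10, "Summary of Adverse Events by System Organ Class and Maximum Grade (Oral Lead-in Period)". It is a Month 12 deliverable on the Safety population and, unlike Table 3.9, its title does not exclude ISRs.

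**The concern.** Moving a partial date back to treatment start or to the first of the month is a sensible way to settle whether an event is treatment-emergent. It is a poor way to settle whether the event arose on oral tablets or after the first injection, because the imputed date is always the earliest one and the lead-in is the earliest period. Every error goes the same way, into the lead-in.

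Table 3.10 is the only listed AE summary confined to the oral lead-in. A reader would use it to see what happened before any long-acting product was given. If it holds post-injection events, it can overstate oral lead-in toxicity. It could even show a reaction to a study-drug injection dated before any injection.

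**Working it through.** The SAP gives no figure on this point, so the printed rules were applied exhaustively.

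**Inputs**
- Imputation rules: section 13.7.2.1. Lead-in window: Table 11.
- First injection on Study Day 30: the default Month 1 target in section 13.3.1, used here as an assumption for everyone. Days 28 and 35 were also run.
- Assumptions not in the SAP: onset uniform over 365 days from treatment start, start dates uniform over a calendar year, no stop date before treatment start, no oral bridging in the month of first injection.

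**Grid.** 365 start dates × 365 onset days = 133,225 event-days. True lead-in: 365 × 29 = 10,585 (7.9%). Truly on or after first injection: 133,225 − 10,585 = 122,640.

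**Day missing (Day 30), post-injection event-days by calendar month of onset**

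| Month of onset | Event-days | Slotted to lead-in |
|---|---|---|
| Month of first injection | 5,713 | 5,348 (94%) |
| Treatment-start month that also contains the injection | 25 | 25 |
| Any later month | 116,902 | 0 |

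The exceptions in the first row are injections given on the 1st. Total moved: 5,348 + 25 = 5,373, or 5,373 / 122,640 = 4.4% of post-injection events. All 10,585 true lead-in event-days stay in, so 10,585 + 5,373 = 15,958 are slotted there, and 5,373 / 15,958 = 34% are false (35% with Day 28, 30% with Day 35).

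**Day and month missing (Day 30).** 76,609 event-days are slotted to the lead-in: 66,795 because the year matches the treatment-start year, and 9,814 because January 1 of the next year falls inside the lead-in. Of these, 76,609 − 10,585 = 66,024 are post-injection. That is 66,024 / 122,640 = 54% of post-injection events moved, and 66,024 / 76,609 = 86% of those slotted to the lead-in (87% with Day 28, 84% with Day 35).

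In no run is a true lead-in event moved out.

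**Example.** Treatment starts 8 July; first injection 6 August (Day 30).
- Onset 20 August, recorded as August: imputed 1 August, lead-in, wrong.
- Onset 20 September, recorded as September: imputed 1 September, not lead-in, right.
- Onset 20 November, year only: imputed 8 July, lead-in, wrong.
- An ISR recorded as August, with no bridging that month: imputed 1 August, five days before any injection.

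**The case against.** Several fair points can be made for the plan.

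- **The first-of-month rule is mostly harmless.** It misplaces events only when the month contains the first injection. In later months it misplaced none of 116,902 event-days. This stands: a reader might infer that first-of-month imputation generally feeds the lead-in, and it does not.
- **A nearly undated event is not certain to be counted as lead-in.** The year must match the treatment-start year with no earlier full stop date, or January 1 must fall inside the lead-in. On the grid, 76,609 / 133,225 = 58% of year-only events are slotted there, not all. This stands.
- **Footnote [a] need not be a contrary policy.** Completely missing dates are not imputed, so there is no date to test against Table 11. The SAP does not say that such events are excluded because their timing is unknown. This stands as to motive. The result is still uneven: a year-only date says little about a period of about a month, yet can be placed in it automatically.
- **No count of partial dates is given.** Year-only onsets may be rare, since AEs are assessed at most visits. The SAP therefore supports saying that Table 3.10 can include post-injection events, not that it does.
- **The consequences are contained.** The study is descriptive with one treatment group, pooled AE tables ignore the lead-in split, listings show dates as captured, and Listing 13 carries phase and period. This limits the severity but does not correct the table.
- **Simply excluding such events would undercount the lead-in.** This stands, and it shapes the fix.

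**Conclusion.** The point holds for two cases, for ISRs and other AEs alike: (a) the day is missing and the month contains the first injection (unless that injection fell on the 1st or, for ISRs, oral bridging moves the date later); and (b) only the treatment-start year is known with no full stop date before treatment start, or a year-only January 1 falls inside the lead-in. In these cases the printed rules assign the lead-in without regard to the first injection.

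The shares of 34% (range 30–35%) for day-missing and 86% (84–87%) for year-only events apply only to partly dated events already slotted to the lead-in. They rest on uniform onset and a first injection between Day 28 and Day 35. They do not estimate how far Table 3.10 is wrong, which depends on an unstated number of partial dates. This is a minor correction, confined to one descriptive table.

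**What to change.** Keep the section 13.7.2.1 imputation for study phase and treatment-emergent status. Add to Table 11:

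- An AE with a partial start date whose possible onset range (bounded by treatment start, the recorded partial date and any known stop date) includes days both before and on or after the first injection is not counted as oral lead-in. It is shown in Table 3.10 in a separate row, or footnoted count, for onset undetermined relative to first injection.
- ISRs to study drug are never assigned to the oral lead-in.

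If Table 3.10 has already been produced, count the affected events and footnote or correct it.

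**Cost.** A Table 11 note, a program condition and one row. Some true lead-in events also move to the undetermined row. On the Day 30 grid, ignoring stop dates, these are 5,366 of 10,585 day-missing event-days (51%; 54% with Day 28, 43% with Day 35), against 5,373 false ones removed, so about one for one. For year-only dates they are 10,150 of 10,585 (96%; 95–96% across the three days), against 66,024 false ones removed. That trade is why these events should be displayed separately rather than dropped. Pooled AE tables do not change.
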